Another therapeutic agent which could potentially promote disc regeneration is bone marrow concentrate (BMC). Bone marrow concentrate is obtained through a simple centrifugation of autologous bone marrow aspirate. Bone marrow aspirate / concentrate has been used extensively in orthopedic clinical settings to promote tissue healing [17,18]. Growth factors, cytokines and pluripotent stem cells within the aspirate are felt to be responsible for the ability of BMC to promote tissue healing in collagen based structures [19,20].

BMC has been used studied in animal and human trials in multiple non-spine orthopedic conditions [19-23]. Results have been promising. BMC has been used in spinal surgery to augment fusion with positive results [18].

Recently bone marrow concentrate has been used in the treatment of discogenic low back pain. The results of a single trial of BMC intradiscal injection for discogenic LBP have been published with 12 and 24 month follow-up [24,25]. Pettine et al. performed a prospective trial using autologous bone marrow concentrate in a single treatment into the intervertebral discs. The study included 26 patients who had at least moderate to severe low back pain with activity for 6 months and at least 3 months of non-operative treatment without significant changes in their symptoms.

Pain and function were evaluated by visual analogue scale (VAS) and Oswestry disability index (ODI) prior to the procedure and at 3, 6, 12 and 24 months post-injection. Average VAS and ODI scores demonstrated significant improvement at all time points. At the two year mark, 81% of the patients avoided surgery. Of the 21 non-surgical patients, the average decrease in pain was 71% at 2 years. The authors also compared pre-procedural MRI disc degeneration levels (Pfirman grade) to MRI findings at 12 months. No discs appeared worse and in 8 patients there was actual improvement in the degree of disc degeneration of at least 1 Pfirman grade at the level injected.

BMC appears to have an excellent safety profile. Pettine et al. reported no significant side effects from intradiscal BMC [24,25]. In addition, no significant adverse events have been attributed to this treatment in multiple animal and human studies published for a variety of orthopedic conditions [19-23, 26].

4. Inclusion/ Exclusion Criteria

4A. Inclusion/exclusion criteria

Inclusion criteria:

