- Chronic low back pain greater than 6 months with low back pain component greater than leg pain component if present.
- Average pain at least 40/100 on Visual analogue Scale (VAS)

- Inadequate response to conservative care including medication, physical therapy, and/or spinal injections.
- Males and females at least 18-55 years old.
 - Rationale for age limit of 55: Based upon the study by Depalma et al. [27], at age 55 and less the predicted probability of a discogenic source of pain is higher than any other source. Beyond 55 years of age, zygapophyseal joints have a higher predictive probability. Therefore, the pre-test probability for a test for discogenic pain beyond this age is considerably lower.
- Have provided informed consent.
- If female subjects are of child-bearing potential, they must be using an acceptable form of birth control.
- Advanced imaging of MRI or CT demonstrating abnormal disc morphology.
- Presumed lumbar discogenic pain based upon either A or B below:
 - A. Positive provocative discography in accordance with SIS guidelines [28].
 - Or
 - B. Both B1 and B2
 - B1. The patient must have MRI findings suggestive of discogenic low back pain including either a high intensity zone region or type 1 or type 2 end plate Modic changes [29-31].
 - B2. Exclusion of other structures as source of pain (see below).

Rationale for not requiring discography for inclusion:

The rationale involves several factors. Although injecting the BMC at the time of discography seems most reasonable, the volume of contrast used for the discography test may reach 3ml, when performed in accordance with SIS guidelines [28]. This leaves an inadequate volume capacity to accommodate much volume of BMC. Secondly, in accordance with SIS guidelines [28] discography requires a negative control disc. Discography is invasive and may have negative detrimental effects on the disc [32]. Therefore, potential harm may exist if discography is performed. BMC is considered to be a very benign substance; it is an autologous tissue unlikely to have any detrimental effects [17, 18, 22].

Subjecting patients to two distinct intradiscal procedures (discography prior to the BMC procedure) is difficult to justify when the purpose of discography

(including injecting a normal control level) would be for qualification of an intradiscal injection of a very likely benign substance.

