With two treatment patients for each placebo patient, 40 treatment and 20 placebo patients will be required to achieve 80% power to detect a difference of 0.35 in the proportion of patients with successful improvement between groups with a chi-squared test at a level of significance of 0.05, assuming the proportion of patients achieving success in the control group is 0.2 (20%) This is based upon the preliminary data calculated success rate (>50% improvement in Pain) from Pettine et al. study [24] was 61%. (Our calculation differs from Pettine et al. as we included surgical patients as failures.) The 95% CI are 44-75% using an n of 40 in our proposed treatment group. The placebo rate is a very well done spinal explanatory study was 13% [33]. The placebo rate from an intradiscal study using intradiscal normal saline was 12.5% and 23.5% using hyaluronic acid (the carrier for the treatment). We therefore used the conservative estimate of a placebo response rate of 20% in this study.

5. Study design/methods/procedures

5A. Summary of research design

A total of 60 patients with randomization 2:1 ratio (treatment : control). Pain and function will be assessed using VAS and ODI. Primary outcome will be percentage of patients in the treatment group compared to the control group at 6 months categorized as a clinical success, at least 50% relief of pain. Secondary outcomes will be comparison of success rates (at least 50% pain relief) at 3 and 12 months. Other secondary outcome will be percentage of patients in the treatment group vs control group with greater than 30% improvement in ODI at 3, 6, and 12

months. Global Perceived Effect (GPE) will also serve as a secondary out come at 3, 6, and 12 months. Medication log and adjunctive treatments will also be recorded and analyzed.

| Randomization process: computer randomization program

Randomization shall be performed through a computer randomization program.

<https://www.random.org/#numbers> (Randomness and Integrity Services Ltd. Dublin, IR.) A random number shall be generated between 1 and 60. For all randomly generated number from 1 to 40, the patient will be assigned to the treatment group. For all randomly generated random number from 41 to 60, the patient shall be assigned to the placebo group.

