The data from the pre and post VAS (0-100 mm) and Oswestry disability index 0-100 will be analyzed from baseline to 3, 6, and 12 months [35]. Categorical data will be used. Primary outcome for success will be considered at least 50% improvement in pain by VAS at 6 months and secondary outcome at 3 and 12 months. Additional secondary outcomes will include 3, 6, and 12 month minimum of 30% improvement in ODI. Further secondary outcomes will also include a minimum of 30%, and 70% improvement in pain at 3, 6, and 12 months. All time point categorical success rates will be compared to placebo group with 95% CI determined. Group data mean pain scores will also be analyzed for each time point using *t*-tests. Global perceived effect will be analyzed for 3,6,12 months on a 5 point scale using categorical data analysis.

Pain medication log at baseline, 3, 6, and 12 months will be analyzed by a simple categorical decrease, increase, or unchanged compared to baseline. Morphine equivalents will not likely be helpful as the majority of the subjects will not likely be on opiate medication. Those patients not on medication at baseline shall not be included in the medication analysis.

Adjunctive treatments: All other therapeutic treatments for LBP during the study period shall be recorded at 3, 6 and 12 months.

5C. Monitoring:

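### ODI is analysed only as a 30% responder rate while means are compared for pain alone; a baseline-adjusted comparison of mean ODI should be added beside it

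*Combined protocol and SAP*

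**What the plan says.** Section 5B opens by saying that the pre and post scores, including "Oswestry disability index 0-100 will be analyzed from baseline to 3, 6, and 12 months", and continues at once with "Categorical data will be used". For ODI it then names one endpoint: "Additional secondary outcomes will include 3, 6, and 12 month minimum of 30% improvement in ODI". Responder rates are compared with placebo at each visit: "All time point categorical success rates will be compared to placebo group with 95% CI determined". The single sentence on means covers pain only: "Group data mean pain scores will also be analyzed for each time point using *t*-tests".

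Section 5A lists the ODI responder rate among the secondary outcomes, with a slightly different cut-off: "greater than 30% improvement in ODI at 3, 6, and 12" months.

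Section 4A sets an entry floor for pain, "Average pain at least 40/100 on Visual analogue Scale (VAS"), but neither the inclusion nor the exclusion list sets one for ODI. Section 3C says of the earlier BMC study: "Average VAS and ODI scores demonstrated significant improvement at all time points". The power statement in section 4F concerns the pain responder endpoint. No power, expected mean, SD or effect is given for ODI.

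**The concern.** ODI is the trial's only disability scale. Reducing a 0-100 score to yes or no discards information, and 40 against 20 patients leave little to spare. The plan adds a comparison of means for pain but not for function, so a real benefit on function is more likely to go undetected or to be estimated imprecisely. If the opening sentence of 5B was meant to cover mean ODI, no method is fixed for it, and the analysis could be chosen or dropped after the results are known.

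A percentage rule without an entry floor also means different things for different patients. Thirty per cent is 3 points from a baseline of 10 and 18 points from a baseline of 60.

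Finally, the two cut-offs disagree at the boundary. A fall from 40 to 28 is 12/40 = exactly 30%, which is a success under 5B and a failure under 5A.

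**Working it through.** **The plan's own figure.** There is none for ODI. The one power claim (4F: 80%, 20% against 55% success, 20 and 40 patients) is for pain. The pooled two-sided formula gives 76.0% for it and the unpooled formula 83.6%. That is a separate matter; only the arm sizes, the chi-squared test and the 0.05 level are used below.

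**Assumed inputs** (none is in the documents): baseline ODI mean m = 35-40; SD 15 at both visits; baseline/follow-up correlation r = 0.5-0.6; placebo change 5 points; uniform benefit 10 points; two-sided 0.05.

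**Responder test.** Success means follow-up ≤ 0.7 × baseline. The quantity follow-up − 0.7 × baseline has mean 0.3m − 5 (placebo) or 0.3m − 15 (BMC), and SD 15 × √(1.49 − 1.4r). At m = 40:

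- r = 0.5: SD 13.33. Placebo Φ(−7/13.33) = 30.0%; BMC Φ(3/13.33) = 58.9%.
- r = 0.6: SD 12.09. Placebo Φ(−7/12.09) = 28.1%; BMC Φ(3/12.09) = 59.8%.

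Pooled chi-squared power = Φ[(d − 1.96 × SE0)/SE1]:

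- r = 0.5: (0.289 − 1.96 × 0.1369)/0.1287 = 0.16, giving 56%.
- r = 0.6: (0.317 − 1.96 × 0.1369)/0.1269 = 0.38, giving 65%.

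**Comparison of means.** SE = s × √(1/20 + 1/40) = 0.2739 × s; power = Φ(10/SE − 1.96).

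| Analysis | s | SE (r = 0.5; 0.6) | Power (r = 0.5; 0.6) |
|---|---|---|---|
| t-test on change | 15√(2 − 2r) = 15.0; 13.4 | 4.11; 3.67 | 68%; 78% |
| Means adjusted for baseline | 15√(1 − r²) = 13.0; 12.0 | 3.56; 3.29 | 80%; 86% |

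**Simulation.** These formulas are normal approximations. Simulating 40 against 20 patients under the same inputs, with scores held within 0-100, gives:

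| Analysis | Power |
|---|---|
| 30% responder, chi-squared | about 60-67% |
| Unadjusted t-test on change | about 66-76% |
| Linear regression adjusted for baseline | about 78-85% |

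Repeat runs move these by about one point. Type I error is about 5% for the responder test and for the adjusted comparison. Taken in that order, leaving the cut-off gains about 6-9 points (66 − 60; 76 − 67) and adjusting for baseline about 9-12 (85 − 76; 78 − 66). Half or more of the gain is therefore adjustment.

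**Other inputs.** With baseline mean 30, 40 or 50, baseline SD 14, follow-up SD 17, correlation 0.4-0.6 and a 12-point benefit, the three powers are 59-73%, 66-86% and 77-88%. If instead half the treated patients respond strongly (a 60% reduction), the responder test has 60-72% and the adjusted comparison 68-79%, a gap of 7-8 points.

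**Small changes counted as success.** Thirty per cent is 6 points at baseline 20, 12 at 40 and 18 at 60. A responder can change by less than 10 points only if baseline is below 10/0.3 = 33.3. The share entering below 20 is Φ(−20/15) = 9.1% at mean 40 and Φ(−15/15) = 15.9% at mean 35. Among simulated responders, however, only about 2-3% changed by less than 6 points and about 6-10% by less than 10. Both thresholds are illustrations, because the documents state no important change in ODI.

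**The case against.** ODI is one of several secondary outcomes and has no stated power. The protocol uses responder success throughout, including for its primary endpoint, so a responder rate for ODI is a deliberate and consistent choice. The size of any loss rests on inputs that the documents do not supply, and against the plan's own kind of test for means, an unadjusted t-test, the loss is modest. All of this stands. It limits the size of the point and argues against demoting the responder rate. It does not explain why means are compared for pain and not for ODI.

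A reader might infer more than the documents support:

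- *That the endpoint counts trivial changes as success.* No threshold for an important change is given, and few simulated responders had small changes. Entry requires pain of at least 40/100 for more than 6 months after inadequate conservative care, so very low baseline ODI is probably uncommon, although nothing excludes it.
- *That the whole power gap comes from dichotomising.* Much of it comes from baseline adjustment, which would be an equally fair suggestion for the pain t-tests.
- *That function is the trial's main supporting claim.* The documents do not rank it so.
- *That the result could not be set beside the earlier BMC study.* The scores are collected and 5B does not forbid reporting means; it names no method for them.

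**Conclusion.** The point holds as a worthwhile improvement to a secondary analysis. The plan names no comparison of mean ODI although it collects the score at every outcome visit and compares means for pain. Under the assumed inputs and a uniform 10-point benefit, a baseline-adjusted comparison has about 18 points more power than the responder test (78 − 60; 85 − 67), of which half or more comes from the adjustment. If benefit is concentrated in half the treated patients, the advantage is about 7-8 points. The direction is the same in every adjusted comparison tried, but the size cannot be established from the documents.

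The missing ODI floor is a minor part: the rule can count a small absolute change as success when baseline is low, and under these assumptions it seldom does. The disagreement between 5A and 5B at exactly 30% is a plain inconsistency that rests on no assumption. Neither matter touches the primary endpoint or the sample size.

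**What to change.** Add to section 5B:

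> Mean ODI at 3, 6 and 12 months will be compared between groups by linear regression adjusted for baseline ODI, with the difference and 95% CI.

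Place it alongside the prespecified 30% responder rate, without demoting that rate. Use one cut-off in 5A and 5B, either at least 30% or more than 30%.

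The cost is one added sentence and one reconciled phrase, settled before unblinding. No new data, visits or patients are needed.

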Rationale for non-intradiscal placebo: In light of theoretical risk of needle injury to the disc [32], it was not felt to be appropriate to have the placebo involve a direct disc injection of normal saline. A normal saline injection into the epidural space using an infraneural (retro-discal) transforaminal needle position as a potential placebo was also considered but felt also to be in appropriate due to the risk of unintentional needle position. The risk of disc puncture with this technique is 5% as well the risk of intrathecal injection is 3% [36]. In addition, a normal saline injection into the epidural space might have some dilutional therapeutic benefit as inflammatory cytokine have been documented in the epidural space [37] and therefore, normal saline may have a dilutional therapeutic benefit.

The patient will be observed clinically for 30 minutes with vital signs obtained upon initially arriving to the recovery room and then every 15 minutes. The patient will be discharged to a companion with written and verbal instructions to include no driving or operating machinery for 12 hours. They will be instructed to call for any concerning symptoms such as redness, swelling, fever, or increase in pain. They will also be instructed to call for any bowel or bladder problems, worsening of low back symptoms beyond day 2, post-treatment severe low back pain at any time, new onset fever, or new or worsening of any lower extremity symptoms. They will be

given clear written and verbal instructions on how to contact our providers with 24 hour availability. They will be offered a prescription for post-procedure pain medication, unless they currently have such medication, such as hydrocodone/ acetaminophen 5/325 mg or oxycodone/ acetaminophen 5/325 mg to take 1-2 tabs q 4-6hrs prn post-procedure pain, #10-20. They will be instructed not to engage in any strenuous activity for two weeks after the treatment.

Anticipated procedure time 60-90 minutes.

The patient will be contacted by telephone during post-treatment week one to monitor for any concerning symptoms or adverse events. The patient will be seen in our office for routine follow-up at post-treatment week 2, 4, and 8 weeks to assess for any adverse events and to monitor progress. At baseline 3,6,and 12 months the patients will complete the VAS, ODI and Global Perceived effect (GPE not performed at baseline) [35,38]. Patients will be seen more frequently if clinically indicated.

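### Section 5B names no test for the 5-point Global Perceived Effect and makes no use of its order; an ordinal test would gain power for a one-directional effect

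*Combined protocol and SAP*

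**What the plan says.** Section 5A makes GPE a secondary outcome: "Global Perceived Effect (GPE) will also serve as a secondary out come at 3, 6, and 12" months. The follow-up schedule in section 5 notes "GPE not performed at baseline", so the analysis compares post-treatment ratings between arms. Section 5B gives the whole method as "on a 5 point scale using categorical data analysis". No test, cut-point or effect measure follows, and the labels of the five levels are not given.

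For VAS and ODI, section 5B says "Categorical data will be used" and then lists responder thresholds: 50%, 30% and 70% for pain, and 30% for ODI. Medication use is "analyzed by a simple categorical decrease, increase, or unchanged compared to baseline", again without a test, and patients on no medication at baseline are left out of that analysis.

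The only tests named in the document are chi-squared (section 4F, in the power calculation for the primary outcome) and t-tests for mean pain (section 5B).

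**The concern.** GPE is an ordered scale, and the effect of interest is a shift towards better ratings. Where the plan wants a dichotomy it states the threshold. For GPE it states none and keeps five points. An analyst following the text would therefore most naturally apply the one categorical test that the plan names to a 2 x 5 table. That test spends 4 degrees of freedom on any difference in pattern and would give the same result if the five levels were relabelled in any order.

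At stake is the chance of detecting a real shift in a trial of 60 patients, at each of three visits. There is also a smaller matter of pre-specification. Chi-squared, an exact test, a cut-point chosen later and an ordinal test all fit the present wording.

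**Working it through.** **The plan's own figure.** There is none for GPE. The only power statement, "40 treatment and 20 placebo patients will be required to achieve 80% power", concerns the primary outcome and "a difference of 0.35 in the proportion of patients with successful improvement between groups" (0.20 versus 0.55). With the pooled proportion (0.20 + 2 x 0.55)/3 = 0.433, the control arm needs [1.96 x sqrt(0.433 x 0.567 x 1.5) + 0.842 x sqrt(0.16 + 0.2475/2)]^2 / 0.35^2 = 21.9. That rounds to 22 + 44 = 66 patients; at 40:20 the formula gives 76% power and exact enumeration 78%. This is a separate matter and does not bear on GPE. Only the arm sizes are carried forward.

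**Inputs.**
- From the plan: 40 and 20 patients, alpha 0.05 (taken as two-sided), five levels.
- Assumed placebo distributions, worst to best level: P1 5/15/45/25/10%, P2 10/25/45/15/5%, P3 20/30/30/15/5%, P4 5/15/60/15/5%.
- Assumed effect: a proportional-odds shift, in which every cumulative odds (this level or worse) in the treatment arm equals the placebo odds divided by the odds ratio.
- Odds ratios 2.7 and 4.5 are log-odds shifts of 1.0 and 1.5. Odds ratio 4.89 is the plan's primary effect carried over to the top two levels: (0.55/0.45)/(0.20/0.80) = 4.89.

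**Formula check, P1.** At odds ratio 2.7 the treatment distribution becomes 1.9/6.5/32.2/36.2/23.2%, so the top two levels rise from 35% to 59%. Let pbar be the category proportions pooled over arms (1/3 placebo, 2/3 treatment) and d the treatment-minus-placebo difference.
- 2 x 5 chi-squared: noncentrality = 60 x (2/9) x sum(d^2/pbar) = 13.33 x 0.286 = 3.82. On 4 df with critical value 9.49, power is 31%.
- Ordinal test: information V = 60 x (2/9)/3 x (1 - sum pbar^3) = 4.44 x (1 - 0.090) = 4.04. Then z = 1.0 x sqrt(4.04) = 2.01, and power = Phi(2.01 - 1.96) = 52%.
- At odds ratio 4.5 the same formulas give noncentrality 8.18 and 62% power, against z = 1.5 x sqrt(4.07) = 3.03 and 86%.

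**Simulated power at 40 versus 20** (rounded; simulation error is about a point):

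| Odds ratio | Placebo distributions | 2 x 5 chi-squared | Top-two dichotomy | Wilcoxon |
|---|---|---|---|---|
| 1 (type I error) | P2-P4 | 4.0-4.5% | about 5% | 4.9-5.1% |
| 2 | P2-P4 | 12-15% | 18-19% | 24-28% |
| 2.7 | P1-P3 | 28-31% | 36-45% | about 50% |
| 3 | P2-P4 | 30-36% | about 43% | 52-59% |
| 4.5 | P1-P3 | 62-66% | 73-77% | about 83% |
| 4.89 | P2-P4 | 64-69% | 77-78% | 84-88% |

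Under P4, the most peaked distribution, simulation at 2.7 and 4.5 gives 25% versus 45% and 58% versus 80%. Both tests are lower, with a similar gap.

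**Sparsity.** If all five levels occur, the placebo row's expected counts sum to 20 and average 20/5 = 4, so at least one is below 5. In simulation about 4 to 6.5 of the 10 cells were below 5. Even so, chi-squared rejected in 4.0-4.5% of null trials. Permutation versions at odds ratio 4.89 gave 68-70% for the unordered test and 84-88% for Wilcoxon. The gap therefore comes from ignoring the order, not from the large-sample approximation.

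**Counter-case.** For a mixed effect, placebo 10/20/40/20/10% against treatment 30/10/20/10/30%, chi-squared has 67% power and Wilcoxon 4%.

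**Medication change.** With three levels (2 df) and an assumed full 40 versus 20, the ordinal gain is about 7-9 points. The real denominator is smaller by an unknown number, because patients on no medication at baseline are excluded.

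**The case against.** The strongest objection is that the plan does not say the categories are unordered. Categorical data analysis as a field includes trend tests and proportional-odds models, and chi-squared is stated only for the binary primary outcome. This stands. A reader might infer that section 5B commits to an unordered test, but the wording supports only that no test is named and that a 2 x 5 chi-squared is the likely default.

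GPE might instead be dichotomised, as pain and ODI are. The gap to Wilcoxon then shrinks to about 50 - 45 = 5 up to 50 - 36 = 14 points at odds ratio 2.7, and 83 - 77 = 6 up to 83 - 73 = 10 points at 4.5. It does not vanish, and a cut-point would still have to be stated.

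A reader might also infer from the sparse table that chi-squared would be invalid here. The simulations do not support that, since its type I error is held.

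Nor is the ordinal test free of any drawback. It has almost no power for a balanced mix of better and worse, and proportional odds adds a model assumption. A mixed effect cannot be excluded: section 6A lists disc degeneration and herniation among the risks of disc puncture, though it calls the risk minimal, and the placebo avoids puncture. Choosing an ordinal test means choosing to look for a one-directional shift, which is a reasonable aim for GPE.

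**Conclusion.** The point holds as a cheap improvement. Section 5B leaves the GPE test open and ignores the order of the scale. Against the most natural reading, an ordinal test gains about 12 to 23 points of power for odds ratios from 2 to 4.89; against a top-two dichotomy the gain is smaller.

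These sizes rest on assumed placebo distributions, a consistent proportional-odds shift and all 60 patients rated. The documents give no GPE figures to replace those assumptions. The direction of the result was the same under all four distributions. The finding does not extend to an invalid test or an inflated error rate. GPE is one of several secondary outcomes, and neither the primary analysis nor the sample size changes.

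**What to change.** In section 5B, state that GPE at 3, 6 and 12 months is compared between arms by the Wilcoxon rank-sum test, or by proportional-odds regression reporting a common odds ratio with 95% CI. Add that counts in each of the five categories are tabulated by arm at each visit, so that a mixed pattern would be seen. The same ordinal test may be used for the three-level medication change, ordered decrease, unchanged, increase, with the number of patients on medication at baseline reported by arm.

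The cost is one or two sentences, with no new data and no extra patients. The price in method is low power for a mixed better-and-worse effect and, if the regression is chosen, the proportional-odds assumption.

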The patients will be blinded to treatment assignment. The patient will follow up for assessment with an investigator who remains blinded to the treatment assignment. Only the physician performing the procedure will be aware of the group assignment.

Based upon previous recommendations for the assessment of blinding success in clinical trials [34] the patients will be queried at 2 weeks whether they believe they have received the active treatment, the placebo, or if they do not know to which group they were assigned.

Treatment: a single intradiscal injection of autologous bone marrow concentrate into suspected painful discs based upon history, image findings and the exclusion of other anatomic structural sources of pain such as z-joints and SIJ.

Placebo: Intramuscular injection of normal saline directly above the transverse process at each suspected discogenic pain level. (The physician performing the procedure will not be blinded, but the assessor for follow up evaluation will be blinded).

A sham bone marrow aspiration will also be performed involving fluoroscopic guidance and anesthetic to the iliac crest. The patient will hear the noise of the bone marrow drill (unattached), while a 21 gauge needle is tapped against the periosteum.

Patients will be screened from a pool of existing patients at a community outpatient spine and musculoskeletal practice. These patients will have had an inadequate response to conservative treatments, some of whom will be considering fusion surgery. Some of these patients will be considering provocative discography through the recommendation of a local surgeon. One of the options discussed will be bone marrow concentrate intradiscal injection under the context of the study. If the patient has any interest in participating in this study, the general risks, benefits and literature will be discussed. The patient will be informed that their status as a patient in the principle investigator's practice and the physician-patient relationship will not be altered regardless of their participation in the study. They will be given a written summary of the study. If they have continued interest, an appointment will be arranged for the verbal and written consent process. Once the consent form process has been completed, the patient will perform the VAS as well as the ODI which will serve as the baseline measurement data [35]. A pain medication query shall be performed as well.

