A medication query shall be performed at baseline 3, 6, and 12 months. In addition, any additional treatments obtained during the follow up period shall be recorded. Other treatments during the study period will be discouraged but not forbidden.

Alternatives to bone marrow concentrate treatment:

- These patients have typically had extensive conservative treatment and may be considering lumbar fusion surgery (or disc replacement) as a possible treatment option. The risks of this type of surgery in the lumbar spine include infection, bleeding, nerve injury, paralysis and death. The most common adverse event or outcome encountered, however, is perceived lack of efficacy or worsening of symptoms after this extensive surgery and recovery period.
- Although these patients have had inadequate pain relief and functional improvements from their prior conservative treatments, they certainly have the alternative of continuing with their current treatment regimen, which may be of some benefit. These treatments often include medications, physical therapy, chiropractic care, and spine injections. The risks of spinal injections, although rarely occurring, include infection, bleeding, nerve injury, paralysis, and death. The risks of the various medications used for pain are medication dependent and are numerous.
- Other types of intradiscal injections are an option. Intradiscal methylene blue has shown early promise in a quality RCT [11] but investigations to replicate their results have been disappointing [12, 13]. Intradiscal steroid may be of benefit for individuals with certain end plate changes on MRI [39] but these positive results have been viewed with extreme caution based on poor results from prior studies [40]. Other regenerative type treatments such as platelet-rich plasma may be also be beneficial [15, 16]. The risks of intradiscal injections, although rare, include infection, bleeding, nerve injury, paralysis, and death.

- “Alternative” or “complementary” medicine treatments such as acupuncture, prolotherapy or homeopathic remedies could also be considered. Serious risks of prolotherapy include paralysis and severe risks of acupuncture include pneumothorax.
- The option of no further treatment may also be a reasonable alternative for some patients.

5B. Analysis of study results:

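### The medication analysis drops patients not on medication at baseline, so a change from none to some is never counted as an increase in either arm

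*Combined protocol and SAP*

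**What the plan says.** Section 5B (Analysis of study results) defines the outcome: "Pain medication log at baseline, 3, 6, and 12 months will be analyzed by a simple categorical decrease, increase, or unchanged compared to baseline". It sets morphine equivalents aside because most patients are not expected to be on opiates, and then restricts the analysis: "Those patients not on medication at baseline shall not be included in the medication analysis".

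Data collection carries no such restriction. At baseline, section 5A says "A pain medication query shall be performed as well", and for follow-up it says "A medication query shall be performed at baseline 3, 6, and 12 months". The design summary at the start of 5A promises "Medication log and adjunctive treatments will also be recorded and analyzed" and does not mention the exclusion.

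Patients without current medication can be enrolled. The criterion in section 4A is "Inadequate response to conservative care including medication, physical therapy, and/or spinal injections", which does not require medication use at entry.

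**The concern.** The outcome has three categories. A patient on no medication at baseline cannot fall into the decrease category, but can fall into either of the others: unchanged if still on none, increase if now on some. The exclusion removes both. It therefore does more than drop patients who have nothing to reduce; it also removes every new start from the only medication analysis that the plan specifies.

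This matters mainly for interpretation. The VAS, ODI and GPE outcomes carry no condition on new medication. A baseline non-user who starts an analgesic and reports at least 50% relief at 6 months is a success on the primary endpoint, and the medication analysis says nothing about that patient. A reader who asks whether pain relief came with new analgesic use gets an incomplete answer.

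**Working it through.** **Reading the rule against the categories.** The documents give no figure for the medication analysis, so there is nothing to reproduce. The main check is logical.

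| Baseline status | Can decrease | Can be unchanged | Can increase | In the planned analysis |
|---|---|---|---|---|
| On medication | yes | yes | yes | yes |
| Not on medication | no | yes | yes | no |

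The number of none-to-some changes counted as an increase is thus zero in each arm, whatever the true number.

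**Can such changes occur?** Yes. Section 5A advises against other treatments during the study but does not prohibit them. At discharge, "They will be offered a prescription for post-procedure pain medication, unless they currently have such medication", so baseline non-users are among those offered it. That supply is small and meant for procedural pain, so it is weak evidence of use at 3 months or later.

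**Does another analysis capture them?** None that is specified. Morphine equivalents are set aside. The adjunctive-treatment paragraph in 5B covers other therapies and says only that they are recorded. Section 5A says they are analysed but gives no method.

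**Illustration of size.** From the documents: 60 patients randomised 2:1, that is 40 BMC and 20 placebo (sections 4F and 5A). Everything else is assumed:

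- s, the share on medication at baseline, is 0.8, 0.6 or 0.4, equal in both arms.
- 20% of baseline users increase, in both arms.
- 10% of BMC and 30% of placebo non-users are on medication at the query.

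Increase rate in all patients = s × 0.20 + (1 − s) × starter rate.

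| s | Excluded (BMC + placebo) | Planned analysis | All patients, BMC | All patients, placebo |
|---|---|---|---|---|
| 0.8 | 8 + 4 = 12 | 20% v 20% | 0.16 + 0.02 = 18% | 0.16 + 0.06 = 22% |
| 0.6 | 16 + 8 = 24 | 20% v 20% | 0.12 + 0.04 = 16% | 0.12 + 0.12 = 24% |
| 0.4 | 24 + 12 = 36 | 20% v 20% | 0.08 + 0.06 = 14% | 0.08 + 0.18 = 26% |

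The hidden difference is (1 − s) × (BMC starter rate − placebo starter rate). At s = 0.6 this is 0.4 × (0.10 − 0.30) = −8 points. With equal starter rates it is zero. With the rates reversed it is +8 points (24% v 16%).

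**Precision.** At s = 0.6 the starters number 16 × 0.10 = 1.6 (BMC) and 8 × 0.30 = 2.4 (placebo). The 95% half-width is 1.96 × √[p₁(1 − p₁)/n₁ + p₂(1 − p₂)/n₂]:

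- 16% v 24% at 40 v 20: 1.96 × √(0.00336 + 0.00912) = 0.219
- 20% v 20% at 40 v 20: 1.96 × √(0.004 + 0.008) = 0.215
- 20% v 20% at 24 v 12 (baseline users only, s = 0.6): 1.96 × √(0.00667 + 0.01333) = 0.277

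The 8-point difference lies well inside a half-width of about 22 points. The last two figures refer to different populations, so the narrower one is not a gain in power for the same question.

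**The case against.** The restriction can be defended. It is prespecified and uses a characteristic fixed before treatment, so the comparison among baseline users remains a fair randomised one. It asks whether existing medication changes, and only baseline users can fall into all three categories. The analysis is supportive, the primary endpoint does not depend on it, and the data are collected, so new starts could be reported afterwards. The illustration rests on chosen inputs. Section 5B also attaches its comparison with placebo and its confidence intervals to success rates; it does not spell out a between-arm comparison of medication change. New drugs might be picked up among adjunctive treatments. Finally, the plan does not define what counts as an increase among baseline users, and the fix leaves that open.

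Most of this stands as a limit on weight. A comparison by arm is the natural reading for medication but is not stated, and the illustration shows a mechanism, not a prediction. Two parts do not answer the point. Being unable to decrease is a reason to restrict the decrease comparison to baseline users, not to drop non-users from the increase comparison. And the adjunctive-treatment route has no specified analysis, nor is it clear that a newly started analgesic would fall under it. Adding starters after unblinding would also be open to challenge in a way that a prespecified rule is not.

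**Conclusion.** The concern holds. As written, the plan counts no change from none to some as an increase, in either arm, and no other specified analysis covers it. The size and direction of any hidden between-arm difference cannot be known from the documents. Under the assumed rates it runs from 4 to 12 points as baseline use falls from 80% to 40%; it is zero if starter rates are equal and changes sign if they are reversed. This is a gap in a supportive analysis, not a bias in the comparison among baseline users or a threat to the primary endpoint. It is worth correcting because the correction is cheap and gives a complete prespecified account of medication increases. It does not add power, and it changes nothing for decreases.

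**What to change.** Replace the exclusion sentence in section 5B with:

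> All randomised patients with a medication query at the time point are included. A patient not on pain medication at baseline is classed as unchanged if on none, and as increase if on any, at the 3, 6 or 12 month query; short-term post-procedure medication no longer in use at the query does not count. The proportion with an increase is compared between arms in all patients; the proportion with a decrease is compared in baseline users.

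This keeps the sponsor's restriction for decreases, where it makes sense. The cost is a few lines of text and two denominators to report at each time point. The queries at baseline, 3, 6 and 12 months already supply the data. What counts as an increase among baseline users remains undefined and could be settled in the same edit.
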